1 INTRODUCTION AND RATIONALE

1.1 Therapeutic Area Background

Coronavirus Disease 2019 (COVID-19) infection presents with respiratory symptoms and fever in the majority of patients.^{1,2} Among patients requiring hospitalization, the majority develop pulmonary infiltrates. The virus that causes COVID-19, SARS-CoV-2, as with SARS-CoV and Middle East respiratory syndrome-related coronavirus (MERS-CoV), can induce an excessive and aberrant non-effective host immune responses that is associated with severe lung pathology, leading to death.²⁻⁴ Similar to patients with SARS-CoV and MERS-CoV, some patients with SARS-CoV-2 develop ARDS with characteristic pulmonary ground glass changes on imaging. In most patients who develop critical disease, SARS-CoV-2 infection is associated with a cytokine storm, with high levels of IL-6 and other proinflammatory cytokines being associated with poor outcomes.^{5,6} Similar cytokine storm pathology and outcomes has been described for SARS-CoV and MERS-CoV.⁷ A recent single arm study in 20 COVID-19 patients in China suggests that targeting IL6 with anti-IL-6 antibody may have clinical benefit,⁸ and several studies are initiating to study anti-IL-6 treatment in a controlled manner.

In patients who develop acute lung injury (ALI)/ARDS due to coronavirus infection who go on to survive intensive care, the excessive immune response leads to long-term lung damage and fibrosis, causing functional disability and reduced quality of life.^{9,10}

An important downstream effect of CGRP release is upregulation and release of IL-6 from a variety of cell types in different diseases.¹¹⁻¹⁸ CGRP also drives T-cell polarization towards a Th17 response.^{17,19-21} Consequently, the treatment of COVID-19 by an agent that blocks the CGRP receptor may provide therapeutic benefit in this disease state by inhibiting the downstream IL-6 and/or Th17 sequelae, and forms the basis of this proposal.

1.1.1 CGRP Background

Calcitonin gene-related peptide, or CGRP, is a pleotropic neuropeptide that is primarily released in response to activation of TRP ion channels.²² Originally, TRP channel physiology focused on its fundamental meaning in sensory neuronal function. However, it is now known that activation of diverse TRP ion channels in multiple cell types results in neuropeptide release and consecutive neurogenic inflammation, with TRPV1²² TRPV4²³ and TRPA1^{2,24} known to be responsible for CGRP release.

The TRP channel is a non-selective cation channel predominately permeable for calcium ion (Ca2+),²⁵ and is directly activated by chemical, thermal (e.g. fever), and mechanical stimuli, including infectious disease stimuli.^{20,26-29} TRP channels are ubiquitously expressed in dienter tissues and cell types and are a key player in the regulation of intracellular calcium. Viruses require Ca2+ for replication and respiratory viruses, including coronavirus, have been reported to increase the expression of these channels in sensory neurons and human bronchial epithelium cells^{25,30,31} to facilitate replication.

As a result of its connection to TRP channel activation, CGRP is released and is pleotropic effects involved in a variety of acute lung injuries diseases.^{32,33} CGRP receptor antagonists have been shown to reduce proximal airway necrosis by 40% and terminal bronchiole necrosis by 50% in chemical acute lung injury.³² Blockade of TRPV4, or downstream CGRP, could be an important therapeutic approach in managing edema and acute lung injury in inflammatory lung diseases.³⁴⁻³⁶

An important downstream effect of CGRP release is upregulation and release of IL-6 from a variety of cell types in different diseases.¹¹⁻¹⁸

CGRP regulates T-cell function via T-cells' interaction with dendritic cells (DCs) and macrophages, both of which express the CGRP receptor.^{37,38} In various diseases in which CGRP signaling becomes dysfunctional, including those induced by aberrant TRP activation, CGRP drives T-cell polarization towards a Th17 response.^{17,19-21} In fact, deletion of a crucial subunit of the CGRP receptor has been shown to ameliorate Th17 autoimmunity.²¹

1.1.2 *Product Development Background*

Details of the clinical and preclinical studies are provided in the most current version of the Investigator's Brochure.³⁹ A summary of the relevant data is presented below.

1.1.2.1 *Non-clinical Pharmacology, Pharmacokinetics, Pharmacodynamics and Toxicology*

[figure not shown]
A series of in vitro and in vivo pharmacokinetic (PK) and metabolism studies were conducted with zavegeptant in rats, dogs, rabbits, mice and monkeys. Safety studies were also performed in rat and monkey to determine tolerability, potential for local irritation, and to assess systemic toxicity. The details of these studies can be found in the Zavegeptant (BHV-3500) Investigator Brochure (IB).³⁹

1.1.2.2 *Clinical Experience*

CCI

[REDACTED]

CCI

1.1.2.3 *Other Clinical/Non-Clinical Studies*

A series of in vitro studies have been performed to investigate CYP-mediated drug interactions. Zavegeptant has been examined for effects in a transporter study.⁴⁰ The details of these studies can be found in the Zavegeptant (BHV-3500) IB.³⁹

1.1.2.4 *Clinical Adverse Event Profile*

1.1.2.4.1 Phase 2/3 Dose Ranging Study (BHV3500-201)

BHV3500-201 is a concluded, pivotal, Phase 2/3, double-blind, randomized, placebo-controlled, dose-ranging study conducted to evaluate the safety and efficacy of zavegeptant (5 mg, 10 mg, or 20 mg) of a single dose of zavegeptant IN versus placebo in the acute treatment of migraine.

No deaths were reported, and no treatment-related SAEs were reported. SAEs were reported on-treatment in two subjects including post-traumatic thrombosis reported in one subject in the zavegeptant 10 mg group, and vestibular migraine reported in one subject in the placebo group. Both events were moderate in intensity and judged by the investigator as not related to study drug.

The overall incidence of AEs was 26.2% (311 of 1,185 subjects) in the zavegeptant groups and 15.4% (62 of 403 subjects) in the placebo group. The incidence of AEs in the zavegeptant groups were as follows: 22.7% (88 of 388 subjects) in the 5 mg group, 24.6% (97 of 394 subjects) in the 10 mg group, and 31.3% (126 of 403 subjects) in the 20 mg group. The majority of AEs were mild in intensity. The table below presents the most frequently reported (2.1% in any zavegeptant group) AEs in the zavegeptant groups.

BHV3500-201 Most Frequently (≥1%) Reported AEs					
No. Treated	(N=388)	(N=394)	(N=403)	(N=1185)	(N=403)
Adverse Event	5 mg	10 mg	20 mg	Overall zavegeptant	Placebo
Dysgeusia	13.9%	13.5%	16.1%	14.5%	3.5%
Nausea	2.6%	4.1%	2.7%	3.1%	0.5%
Nasal Discomfort	1.3%	1.3%	5.2%	2.6%	0.2%
Throat Irritation	1.0%	1.0%	2.2%	1.4%	0.0%
Vomiting	0.3%	1.8%	1.7%	1.3%	0.2%
UTI	0.8%	1.0%	2.0%	1.3%	1.2%

Nasal inspection conducted at screening, baseline and end of treatment showed no clinical evidence of nasal mucosal injury. No subject had AST or ALT > 3x ULN or bilirubin > 2x ULN in any treatment group.

The first-generation small molecule CGRP antagonists (e.g. telcageptant and MK-3207), have shown effects on elevated transaminases and hypertension. The liver effects of these compounds were thought to be related to the chemical structures and off-target effects of antagonizing CGRP receptors⁴¹.

Additional information with next generation monoclonal antibodies targeting CGRP receptors (e.g. Airomivig) and other small molecules (e.g. Ubrelvy and Nurtec ODT) have not shown similar liver safety issues. Zavegeptant is a third-generation CGRP receptor antagonist that is structurally unrelated to the first-generation small molecule CGRP receptor antagonists. Liver effects have not been observed with zavegeptant; however, liver safety and blood pressure will be monitored in this study.

1.2 Study Rationale

There is an urgent need to assess both antiviral mechanisms but also host innate mechanisms to combat the COVID-19 pandemic.^{5,42} Given the urgent need to test novel mechanisms to combat COVID-19 infection, the pleiotropic function of CGRP as a key mediator of the neuro-immune system warrants assessment of the potential for CGRP-antagonism in mitigating the hyper-immune disease characteristic of serious COVID-19 infection. This study will assess the hypothesis that antagonizing CGRP receptors in a variety of neural and immune cells within the respiratory tract in the setting of COVID-19 infection will decrease both acute inflammation and edema formation and reduce the subsequent risk of developing interstitial lung diseases (ALI/ARDS) resulting from a hyper-inflammation immune response.

1.3 Dosing Rationale

1.3.1 Zavegeptant Properties

Zavegeptant has multiple properties which render it an ideal molecule for near-term treatment of COVID-19, including (as detailed below), high CGRP receptor affinity, clinical proof-of-concept in migraine for 10 mg intranasal dose, ~6 hour half-life, hospital- and patient-friendly Aptar device usable in ventilation patients, clinical safety with up to 14 days of dosing, Good Manufacturing Practice (GMP) clinical supplies available now, and high aqueous solubility with potential for alternate (i.v., p.o.) formulations:

- Ultra-high affinity for the human CGRP receptor ($K_i = 0.023$ nM) that can displace CGRP from the receptor and blocks the effects of ongoing CGRP release
- Clinical efficacy already demonstrated with 10 mg intranasal dose in the acute treatment of migraine; showing ability block a human disease state associated with high CGRP release
- Short half-life of ~6 hours allows it to be withdrawn and quickly cleared if needed, while also providing durable CGRP receptor occupancy with 8 hour dosing (see Section 1.3.2 Rationale for Dose Selection)
- Intranasal route of delivery that's usable even in patients on ventilation or nasal cannula respiratory support
- The device is familiar, simple to use, disposable, Aptar nasal spray single-shot technology that's already used in hospital settings to treat opioid overdose (NarcanTM)
- Safety and tolerability of nasal zavegeptant have already been demonstrated in humans with multiple doses up to 40 mg daily for 8 days and 20 mg daily for 14 days. The selected zavegeptant dose of 10 mg IN every 8 hours is expected to produce a geometric mean Cmax of 13 ng/mL and AUC over 24 h of 92.7 ng·h/mL (extrapolating from 14 days of dosing up to 10 mg IN once daily (QD) in Study 3500-102). The highest geometric mean Cmax and AUC over 24 h obtained in Study 3500-102 after dosing 20-40 mg IN for up to 14 days were 24.6-40.9 ng/mL and 87.9 to 94.2 ng·h/mL, respectively. Thus, zavegeptant 10 mg every 8 hours IN is expected to produce a Cmax at least 2-3 fold lower and an AUC over 24 hours similar to that produced by the highest doses given to humans for up to 14 days.
- GMP clinical supplies are currently on-hand and available (diverting units from our planned second Phase 3 migraine study)
- High aqueous solubility (> 300 mg/mL) provides for multiple routes of administration; upon successful proof-of-concept can be readily reformulated as intravenous, subcutaneous or oral agent to provide dosing options for inside and outside the hospital setting

1.3.2 **Rationale for Dose Selection**

Zavegeptant 10 mg IN delivered every 8 hours provides durable coverage for CGRP receptor occupancy to test the effect on COVID-19:

- Human PK data were used to conduct steady state simulations
- CCI [REDACTED]
- CCI [REDACTED]
- The clinical safety and tolerability of nasal zavegeptant have already been demonstrated in humans with multiple doses up to 40 mg daily for 8 days and 20 mg daily for 14 days. The selected zavegeptant dose of 10 mg IN every 8 hours is expected to produce a Cmax at least 2 to 3-fold lower than, and an AUC over 24 hours similar to, that produced by the highest doses given to humans over 14 days (see details in Section 1.3.1).

CCI [REDACTED]

CCI [REDACTED]

CCI

CCI

1.3.3 *Rationale for Including Patients with Renal Impairment*

Zavegeptant is metabolically stable and primarily excreted unchanged as parent compound. A recently completed rat ADME study where [14C]-BHV-3500 was intravenously administered to rats⁴⁴ showed that the majority (~85% dose) of radioactivity was recovered during the first 48 hours with feces (64%) as the major route of elimination and a more minor contribution via renal (24%) elimination.

CCI

Consistent with these results, in the human zavegeptant MAD and SAD studies,³⁹ there was no evidence of renal injury.

Subjects with estimated creatinine clearance ≥ 30 mL/min will be allowed into the study. Subjects who develop eGFR <15 mL/min while on study should be discontinued from the study drug.

1.4 *Research Hypothesis*

Zavegeptant reduces and slows the progression of the disease and improves overall outcome of COVID-19 infection.

2 STUDY OBJECTIVES

2.1 Primary Objective

To compare the efficacy of zavegeptant (BHV-3500) to placebo, in subjects hospitalized with COVID-19 infection requiring supplemental oxygen, using a six-point rating scale at Day 15.

2.2 Secondary Objectives

2.2.1 Key Secondary Objectives

1. To compare zavegeptant to placebo on the proportion of subjects alive and off of oxygen at Day 29.
2. To compare zavegeptant to placebo on the proportion of subjects requiring initiation of invasive mechanical ventilation, non-invasive ventilation or use of high flow nasal cannula through Day 29.
3. To compare zavegeptant to placebo on the proportion of subjects admitted into an intensive care unit (ICU) through Day 29.

2.2.2 Other Secondary Objectives

1. To examine the safety of zavegeptant, relative to placebo, as reflected by the number of: deaths; SAEs; severe AEs; and Grade 3 or 4 laboratory test abnormalities.
2. To examine the safety of zavegeptant, relative to placebo, as reflected by the incidence of severe or life-threatening bacterial, invasive fungal, or opportunistic infections through Day 29.
3. To examine the safety of zavegeptant, relative to placebo, as reflected by the incidence of intranasal administration reactions through Day 29.
4. To examine the safety of zavegeptant, relative to placebo, as reflected by the proportion of subjects who develop a significant loss of renal function, defined as at least 50% reduction in eGFR from baseline.

CCI

[REDACTED]

[REDACTED]

[REDACTED]

[REDACTED]

CCI

3 STUDY ENDPOINTS

3.1 Primary Endpoint

Efficacy will be measured by the difference between treatment groups in the mean 6-point severity rating at Day 15. The severity ratings are:

1. Death
2. Hospitalized, on invasive mechanical ventilation or ECMO
3. Hospitalized, on non-invasive ventilation or high flow oxygen devices
4. Hospitalized, requiring supplemental oxygen
5. Hospitalized, not requiring supplemental oxygen
6. Not hospitalized

Six point severity ratings are from the 6-point ordinal rating scale eCRFs. Deaths through Day 15 from AE/SAE and subject disposition CRFs are also taken into account.

3.2 Secondary Endpoints

Procedures are from concomitant procedures eCRFs. Deaths are determined from the following eCRFs: 6-point ordinal severity rating scale; AE/SAE; and subject disposition.

3.2.1 Key Secondary Endpoints

1. Proportion of subjects who have a 6-point severity rating of 5 or 6, are alive, and do not use supplemental oxygen as a procedure at Day 29.
2. Proportion of subjects who have a 6-point severity rating of 2 or 3, or use any ventilation or high-flow nasal cannula as procedures, on any day through Day 29.
3. Proportion of subjects admitted into an ICU on any day through Day 29 from AE/SAE eCRFs.

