	
5. Subjects must have laboratory-confirmed SARS-CoV-2 infection as determined by PCR-based commercial or public health assay6. Subjects must have symptoms that require hospitalization with supplemental oxygen and or non-invasive ventilation as determined by the admitting physician. The maximum nasal cannula O₂ concentration should be determined by the treating clinician and the limitations of the specific equipment7. Subjects must be willing and able to comply with study-related procedures/assessments
Exclusion Criteria	
1. Subjects in immediate need of invasive mechanical ventilation or extracorporeal membrane oxygenation (ECMO)2. Subjects with an estimated glomerular filtration rate (eGFR) of < 30 mL/min, at the Screening Visit3. Prisoners or subjects who are involuntarily incarcerated4. Subjects who are participating in any other investigational clinical trial while participating in this clinical trial5. Subjects under the age of 18 years6. Subjects who are pregnant (all potential female enrollees to have negative pregnancy test prior to investigational product [IP] administration)7. Subjects with multi-organ failure8. Subjects who have received more than 48 hours of supplemental oxygen prior to randomization9. Subjects with prior significant pulmonary disease (e.g., severe chronic obstructive pulmonary disease [COPD]/ interstitial lung disease [ILD]/congestive heart failure [CHF]/idiopathic pulmonary fibrosis [IPF]) are excluded10. Subjects receiving investigational therapies as part of a formal clinical trial for the treatment of COVID-19. During the course of this study, investigational therapies that may become “standard of care” to treat COVID-19, but are not part of a clinical trial, are allowed11. Subjects who are on long-acting CGRP monoclonal antibodies including Aimovig® (erenumab), Emgality® (galcanezumab), Ajovy®

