	
(fremanezumab), and Vyepti® (eptinezumab). Additionally, the investigational oral CGRP receptor antagonist, atogepant, that is taken daily is excluded. Oral CGRP receptor antagonists, Nurtec® ODT (rimegepant) and Ubrelvy™ (ubrogepant) that are typically used PRN infrequently will not be excluded as long the subject was not taking them on a daily basis and does not take them during the current study.
 
12. Subjects who are unlikely to survive for more than 48 hours from the Screening Visit
 
13. Subjects with any of the following abnormal laboratory values at screening: aspartate aminotransferase (AST) or alanine aminotransferase (ALT) greater than 5x upper limit of normal (ULN) or bilirubin greater than 2x upper limit of normal
 
14. Subjects with known active tuberculosis (TB), history of incompletely treated TB, suspected or known extrapulmonary TB
 
15. Subjects with suspected or known systemic bacterial or fungal infections. However, empiric antibiotics are permitted
 
16. Subjects who have participated in any clinical research study evaluating an IP or therapy within 3 months and less than 5 half-lives of IP prior to the screening visit
 
17. Subjects with any physical examination findings and/or history of any illness that, in the opinion of the study investigator, might confound the results of the study or pose an additional risk to the subject by their participation in the study

Primary Objective:	To compare the efficacy of zavegeptant (BHV-3500) to placebo, in subjects hospitalized with COVID-19 infection requiring supplemental oxygen, using a six-point rating scale at Day 15
Secondary Objectives	
Key Secondary Objectives
 
1. To compare zavegeptant to placebo on the proportion of subjects alive and off of oxygen at Day 292. To compare zavegeptant to placebo on the proportion of subjects requiring initiation of invasive mechanical ventilation, non-invasive ventilation or use of high flow nasal cannula through Day 293. To compare zavegeptant to placebo on the proportion of subjects admitted into an intensive care unit (ICU) through Day 29 
Other Secondary Objectives

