5.2 Inclusion Criteria

1. Subjects must provide informed consent in accordance with requirements of the study center's IRB or ethics committee, prior to the initiation of any protocol-required procedures.
2. Subjects must agree to provide all requested demographic information (i.e. gender, race).
3. Subjects must be able to read and understand English or Spanish.
4. Subjects must be over the age of 18 years.
5. Subjects must have laboratory-confirmed SARS-CoV-2 infection as determined by PCR-based commercial or public health assay.
6. Subjects must have symptoms that require hospitalization with supplemental oxygen and/or non-invasive ventilation as determined by the admitting physician. The maximum nasal cannula O₂ concentration should be determined by the treating clinician and the limitations of the specific equipment.
7. Subjects must be willing and able to comply with study-related procedures/assessments.

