5.3 Exclusion Criteria

1. Subjects in immediate need of invasive mechanical ventilation or extracorporeal membrane oxygenation (ECMO).
2. Subjects with an eGFR of < 30 mL/min, at the Screening Visit
3. Prisoners or subjects who are involuntarily incarcerated
4. Subjects who are participating in any other investigational clinical trial while participating in this clinical trial

5. Subjects who are under the age of 18 years
6. Subjects who are pregnant (all potential female enrollees need to have a negative pregnancy test prior to IP administration)
7. Subjects with multi-organ failure
8. Subjects who have received more than 48 hours of supplemental oxygen prior to randomization
9. Subjects with prior significant pulmonary disease (e.g., severe COPD/ILD/CHF/IPF) are excluded
10. Subjects receiving investigational therapies as part of a formal clinical trial for the treatment of COVID-19. During the course of this study, investigational therapies that may become “standard of care” to treat COVID-19, but are not part of a clinical trial, are allowed.
11. Subjects who are on long-acting CGRP monoclonal antibodies will be excluded including Aimovig® (erenumab), Emgality® (galcanezumab), Ajovy® (fremanezumab), and Vyepti® (eptinezumab). Additionally, the investigational oral CGRP receptor antagonist, atogepant, that is taken daily will also be excluded. Oral CGRP receptor antagonists, Nurtec® ODT (rimegepant) and Ubrelvy™ (ubrogepant) that are typically used PRN infrequently will not be excluded as long the subject was not taking them on a daily basis and does not take them during the current study
12. Subjects who are unlikely to survive for more than 48 hours from the Screening Visit
13. Subjects with any of the following abnormal laboratory values at screening: aspartate AST or ALT greater than 5x ULN or bilirubin greater than 2x ULN
14. Subjects with known active TB, history of incompletely treated TB, suspected or known extrapulmonary TB
15. Subjects with suspected or known systemic bacterial or fungal infections. However, empiric antibiotics are permitted
16. Subjects who have participated in any clinical research study evaluating an IP or therapy within 3 months and less than 5 half-lives of IP prior to the screening visit

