5.4 Prohibited and Restricted Concomitant Medications/Procedures

Investigational therapies as part of a formal clinical trial for the treatment of COVID-19 are prohibited during the course of this study. However, if during the course of this study investigational therapies become “standard of care” to treat COVID-19, they are allowed.

Long-acting CGRP monoclonal antibodies Aimovig (erenumab), Emgality (galcanezumab), Ajovy (fremanezumab), and Vysepti (eptinezumab) are not allowed in the trial. A minimum 30-day washout period for these drugs is appropriate, prior to randomization. Additionally, the investigational oral CGRP receptor antagonist, atogepant, that is taken daily will also be excluded. Oral CGRP receptor antagonists, Nurtec ODT (rimegepant) and Ubelyv (ubrogepant) that are typically used PRN infrequently will not be excluded as long the subject was not taking them on a daily basis and does not take them during the current study.

Prior to the Baseline Visit (randomization), if a subject has been on non-invasive supplemental oxygen for more than 48 hours, they should not be randomized. However, if a subject progresses to requiring mechanical ventilation (invasive or non-invasive) after randomization, they will remain on the study, per the Investigator's judgement.

Subjects with renal impairment who have an eGFR \geq 2. 30mL/min are allowed into the study. Subjects who develop an eGFR $<$ 15mL/min while on the study should be discontinued from the study drug.

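### Key secondary endpoint 2 counts patients already on non-invasive ventilation or high-flow oxygen at first dose as events, although its objective is to measure initiation of ventilation

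*Protocol*

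**What the plan says.** Key secondary objective 2 (Protocol 2.2.1, repeated in the synopsis) is the "proportion of subjects requiring initiation of invasive mechanical ventilation, non-invasive ventilation or use of high flow nasal cannula through Day 29". Section 3.2.1 turns this into the proportion with a "6-point severity rating of 2 or 3, or use any ventilation or high-flow nasal cannula as procedures, on any day through Day 29".

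On the 6-point scale in section 3.1, rating 3 is "Hospitalized, on non-invasive ventilation or high flow oxygen devices" and rating 2 is invasive ventilation or ECMO. Section 6.4.1 has the scale rated every day in hospital.

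Inclusion criterion 6 (section 5.2) reads: "Subjects must have symptoms that require hospitalization with supplemental oxygen and/or non-invasive ventilation as determined by the admitting physician". The synopsis has the same criterion. The only exclusion on respiratory support (exclusion 1, section 5.3) concerns immediate need of invasive ventilation or ECMO. No criterion keeps out a patient rated 3.

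Section 9.3.3 tests the key secondary endpoints in the efficacy set by the Holm procedure at 0.05, once the primary endpoint is significant. Section 9.2 defines that set as subjects randomized only once who received at least one dose, with no condition on the baseline rating.

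**The concern.** The objective asks who goes on to need ventilation. The endpoint asks who was on ventilation or high flow at any time up to Day 29, including from the start. Eligibility allows the two to differ: a patient who enters on non-invasive ventilation and is still on it after the first dose meets the endpoint, even if the next change is recovery and discharge.

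Such patients cannot contribute to a treatment difference. They raise the event rate equally, in expectation, in both arms, so they shrink the risk difference and lower power on one of three formally tested key secondary endpoints. The reported proportion also mixes support present at entry with support started on study, so it does not answer the stated objective whatever its size.

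The wording conflict is firm for non-invasive ventilation. For high-flow nasal cannula the objective says use rather than initiation, so the conflict there is arguable, although the dilution is the same.

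**Working it through.** **Reading the text.** Three statements in the current protocol determine the point.

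1. Objective 2 (2.2.1, synopsis): new ventilation.
2. Endpoint 2 (3.2.1): rating 2 or 3, or a ventilation or high-flow procedure, on any day, with no baseline condition there or in the efficacy set.
3. Inclusion 6 (5.2, synopsis): non-invasive ventilation at entry is allowed, and that is rating 3.

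Section 5.4 speaks of what happens "if a subject progresses to requiring mechanical ventilation (invasive or non-invasive) after randomization". It treats non-invasive ventilation as a later worsening, which fits the objective better than the endpoint.

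**Inputs.** From the protocol: 120 patients, 80 zavegepant and 40 placebo (9.1); alpha 0.05 with Holm (9.3.3). Sidedness is not stated for these tests; two-sided is assumed. The protocol gives no event rate, effect or power for this endpoint, so there is no figure to reproduce. Assumed here: the share b on rating-3 support at first dose, and the true event rates p_placebo and p_drug among the others. Section 9.1 expects patients generally to be in category 4, so b is probably small. Table 2 describes people at initial testing and does not bound b.

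**Dilution.** Observed rate = b + (1 − b)p in each arm, so

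observed difference = (1 − b)(p_placebo − p_drug).

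For 30% vs 12% the 18-point difference becomes 17.8, 17.6, 17.1, 16.2 and 14.4 points at b = 1%, 2%, 5%, 10% and 20%. Those shares are about 1, 2, 6, 12 and 24 of the 120 patients.

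**Power.** Two-proportion z-test, pooled variance under the null and unpooled under the alternative:

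power = Φ[(d − 1.96·SE0)/SE1].

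Worked case, 30% vs 12%, b = 10%:

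- As written: 0.10 + 0.90 × 0.30 = 0.370 and 0.10 + 0.90 × 0.12 = 0.208, so d = 0.162. With 40 and 80 patients the pooled rate is 0.262, SE0 = 0.0852 and SE1 = 0.0888. (0.162 − 1.96 × 0.0852)/0.0888 = −0.06, so power is 48%.
- At-risk patients only: 36 and 72 patients, d = 0.18, pooled rate 0.18, SE0 = 0.0784, SE1 = 0.0854. (0.18 − 1.96 × 0.0784)/0.0854 = 0.31, so power is 62%.

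Power in %, as written vs at-risk only:

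| b | 30% vs 12% | 30% vs 15% | 40% vs 20% |
|---|---|---|---|
| 0 | 66 | 49 | 64 |
| 1% | 64 vs 66 | 47 vs 49 | 62 vs 64 |
| 2% | 62 vs 66 | 46 vs 48 | 61 vs 63 |
| 5% | 56 vs 64 | 41 vs 47 | 57 vs 62 |
| 10% | 48 vs 62 | 35 vs 45 | 50 vs 60 |
| 20% | 35 vs 57 | 25 vs 42 | 39 vs 55 |

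The at-risk figures already carry the smaller denominator. At the first Holm step (0.05/3 = 0.0167), for 30% vs 12%, the pairs are 46 vs 50, 40 vs 49, 32 vs 46 and 21 vs 42% at b = 2%, 5%, 10% and 20%. To regain the 66% power of b = 0 with the endpoint as written, the total would have to rise from 120 to 134, 154, 191 and 280 at those shares.

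**Simulation.** With 200,000 trials for 30% vs 12%, and the number on support at entry drawn at random in each arm, power as written was 62.4, 56.8, 48.2 and 34.8% at b = 2%, 5%, 10% and 20%. For at-risk patients only it was 66.4, 64.9, 62.8 and 58.0%. This agrees with the formula within one point, so chance imbalance in b is already in these figures and is no further cost.

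**The case against.** The strongest reply has four parts.

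First, the objective says use of high-flow nasal cannula and the endpoint counts use, so for high flow the two can be read as consistent. That stands: the firm contradiction is for non-invasive ventilation. But rating 3 pools the two, so the pre-dose rating cannot separate them and one rule has to cover both.

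Second, the size rests on assumption. That also stands. Neither b nor the event rates are in the protocol, and the 10% and 20% rows are illustrations that sit awkwardly with the section 9.1 expectation. That expectation is not an eligibility rule, however, and inclusion 6 expressly allows the exception.

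Third, entry on non-invasive ventilation does not make a patient an event with certainty. Inclusion 6 rests on the admitting physician's judgement, and someone weaned before the first dose need not count if only study days are meant. This is right, and b should be read as the share still on support at first dose.

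Fourth, any such support through Day 29 in all dosed patients is a valid randomized comparison, and rewording the objective would remove the contradiction. That is true, and type I error is intact. But rewording alone leaves the dilution and gives up the question of who newly needs ventilation.

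The unseen SAP and the redacted part of section 9.3.3 may hold further analyses, but the endpoint wording in section 3.2.1 would still conflict with its objective.

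**Conclusion.** The point holds and should be fixed. Followed exactly, key secondary endpoint 2 does not measure its stated objective, and it fixes as events any patients still on non-invasive ventilation or high flow at first dose. The expected risk difference falls by the factor (1 − b).

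Under the three assumed pairs of rates, the power lost relative to an at-risk analysis is about 1 to 8 points for b up to 5%, 10 to 14 points at 10%, and 16 to 22 points at 20%. Since section 9.1 points to a small b, the likely loss is modest. The mismatch with the objective does not depend on b. The primary endpoint is not touched.

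**What to change.** In section 3.2.1, item 2, count only ventilation or high-flow support newly started after the first dose, among efficacy-set patients not on such support at the last pre-dose 6-point rating. Use the Screening rating, or the Day 1 rating only if it is timed before dosing: Visit Day 1 begins at the first dose (4.1), so a post-dose rating should not serve as baseline.

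Alternatively, keep all patients and, for those rated 3 before dosing, count only escalation to rating 2.

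Either way, amend objective 2 in 2.2.1 and the synopsis so that initiation clearly covers high flow, and carry the wording into the SAP.

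The cost is mainly wording, because the Screening rating is already collected. The first option needs a clause in section 9.3.3 for the subset, and it shrinks the denominator: 38 vs 76 at b = 5%, 36 vs 72 at 10%. It also leans on a Screening rating that may be up to 48 hours old, since section 4.3.1 captures procedures only from the first dose, apart from the start of supplemental oxygen.

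The alternative keeps 40 vs 80 but may gain less. With 30% vs 12%, if 30% of those rated 3 escalate in both arms, the rates are 30% and 0.30b + 0.12(1 − b). Power is then 65, 64, 61, 56 and 46% at b = 1%, 2%, 5%, 10% and 20%, against 48% as written at b = 10%. If the drug works equally well in those patients, it stays at 66%.
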